Protocol Title: The Role of HMGB-1 in Chronic Stroke

Principal Investigator: [name]

Sub-Investigator: [name]
[name]

Study Coordinator: [name], MS

Introduction

The acute pathophysiology of stroke depends on the innate immune response that begins in a clotted vessel and overwhelms the perivascular and parenchymal affected regional anatomic sector with all of the effector molecules arising from mostly pro-inflammatory cascades. The chronic pathophysiology of stroke is less clear as the innate inflammatory response fades and matures into an adaptive immune response. We want to investigate whether the pro-inflammatory circumstances extend over longer time in patients with stroke by measuring a candidate serum cytokine – HMGB-1 – that is secreted long after an initial insult, causes organ damage, and can be inhibited. Building on the work of the [name] lab here at Feinstein on sepsis [1], and working in the [name] lab we have developed new information about the effect of HMGB-1 on the brain. **We hypothesize that persistent HMGB-1 serum levels in patients with stroke retard functional recovery.** A first step in the test of this hypothesis is to gather serum data in patients with stroke longitudinally. Because we will have collected timed serum samples and stored them in the bio-repository at Feinstein, the hypothesis will be enriched by reexamining the serum samples for other known cytokines, other danger associated pattern molecules (DAMP), and growth factors that may also contribute to a prolonged inflammatory state for some stroke victims. If it turns out that in some patients the inflammatory condition wanes soon after the acute stroke then it will be important to determine the functional outcome compared to those in whom the inflammatory condition persists. While not in the scope of this particular protocol, we have long experience using modern interactive robotic techniques to measure and also to enhance motor function in patients recovering from stroke [2, 3], as our long term goal is to influence future stroke-rehabilitation practice.

Specific Aims

As a first step in achieving a long-term goal to improve stroke recovery, we will determine when and how long the circulating HMGB-1 levels are elevated in patients with stroke. We will also compare the cytokine levels of individuals after stroke with those of health, age-matched controls. We will:

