We will obtain blood samples from 100 consecutive patients with ischemic or hemorrhagic stroke admitted to the Northwell stroke service. As we are interested in assay of HMGB-1 from the time from stroke, the admission sample timing with respect to stroke will be noted and we will obtain subsequent blood samples at 7, 14, 30 and 90 days after the time that the stroke occurred. So if the patient comes in 24- or 48-hours after the onset of symptoms, we will collect the admission sample and collect the 7-day sample 6 or 5 days after admission respectively. Given the challenges of collecting samples within a 24 hour time period, the collection window will be extended such that day 7 and day 14 samples will be collected plus or minus one day of the target (e.g. between day 6-8 or day 13-15, respectively) and day 30 and day 90 samples will be collected plus or minus 7 days of the target (e.g. between day 23-37 and day 83-97, respectively). Each of the 5 samples will be 4 cc each (green top tube). We will also obtain a one-time DNA sample, via the collection of a 10cc lavender tube (EDTA) at the time of the first sample collection. If this is not possible we will collect this sample at the time of a subsequent research blood sample collection. The total volume of blood drawn for each study subject will be no more than 30 cc over the duration of the study. Additionally, we will collect a one-time blood sample from up to 30 healthy, age-matched controls. Control subjects will be NSLIJHS employees, members of the local community recruited with the Northshore Recruitment Registry and GAP Registry recruitment tools, and enrolled subjects' family members recruited by the Research Coordinator and Principal Investigator. Each control sample will be 4cc total (green top tube)

The blood will be centrifuged and prepared for HMGB-1 analysis by NS-LIJ Biorepository staff. If we miss sample collection across the 7, 14, 30, and 90 day time points the available collected samples from a subject will be analyzed. We will measure HMGB-1 and if the levels are elevated (>20ng/ml) we will return to the banked samples in the bio-repository to repository to assay samples for IL-1, IL-6, IL-8, IL-10, TNF and BDNF, all molecules known to be stimulated by HMGB-1 secretion [4, 5].

The following data will be collected for each subject with stroke:

- Age (at time of stroke)
- Gender
- Stroke risk factors (history of hypertension, smoking, estrogen supplements)

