- Concurrent infections (at time of stroke)
- Stroke type (ischemic or hemorrhagic)
- Stroke location
- Stroke severity (NIH Stroke Scale)
- Stroke outcome (Rankin scale) – measured at admission & discharge
- Contact information
- Medical record number

Inclusion criteria:

- All patients admitted to the stroke service at Northwell will be eligible for inclusion in this pilot study.
- Patients \geq 18-years of age

Exclusion criteria:

- Patients <18-years of age

The following data will be collected for each control subject:

- Age (at time of stroke)
- Gender
- Stroke risk factors (history of hypertension, smoking, estrogen supplements)
- Concurrent infections (at time of stroke)
- Contact information

Inclusion criteria:

- Patients \geq 18-years of age
- No report of stroke risk factors (hypertension, smoking, estrogen supplements) or concurrent infections during screening at time of participation.

Exclusion criteria:

- Patients <18-years of age
- Report of stroke risk factors or concurrent infections during screening at time of participation.

Because of the collaborative efforts of the Department of Neurology and the Physical Medicine and Rehabilitation groups we will be able to track the patients from the acute care facility to the rehabilitation units. We know that the combined admissions to the stroke units at the two facilities are nearly 900 patients per annum. We also know that the patients often stay within the greater Northwell Health System and that over 700 patients with stroke are admitted to the rehabilitation units.

Blood sampling for acute stroke subjects will take place on the subjects' in-patient units during their stay in Northwell Health System. We expect, as the average length of stay is 10 days, to collect an admission and day 7 sample. Many patients with stroke are transferred to the rehabilitation service and we expect to collect blood samples for day 14 and 30 on those services. The average length of stay for a patient with stroke on an in-patient rehabilitation unit is 30 days. We are set up in the CRC to collect the 90 day sample and the control subjects' samples. We will ask patients to return to the CRC for this sample collection.

Banking of samples for future use:

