1. HMGB-1
2. Downstream cytokines activated by HMGB-1 including: TNF;IL-1; IL-6; IL-8; IL-10; and growth factor, BDNF.

3. Compare the level of cytokines individuals with acute stroke with those of age-matched, healthy controls. In order to establish baseline cytokine levels, we will collect serum samples from healthy, age-matched controls and assay them for HMGB-1, IL-1, IL-6, IL-8< IL-10, TNF, and BDNF. We predict that cytokine levels will be negligible in healthy subjects and their samples will serve as a control for individuals post-stroke.

Statistical Methods.

This will be a prospective pilot study of patients diagnosed with acute stroke. We will obtain serial blood samples (admission, 7, 14, 30, 90 d after stroke) to examine whether the blood levels of HMGB-1, and TNF,IL-1, IL-6, IL-8, IL-10, and BDNF are elevated, and if they are, determine their temporal characteristics.

Recruitment of patients with stroke will take place among those who admitted to North-Shore and LIJ hospital stroke service.

Specific Statistical Aims. In this pilot we will gather information from patients in the acute phase of stroke and the early recovery phase of stroke. We aim to measure over a three month period the HMGB-1 level, and the downstream pro-inflammatory cytokines such as TNF, IL-1, IL-6, IL-8 and IL-10, and also the growth factor BDNF. We plan to evaluate these serum levels in 100 patients. This data will permit a formal estimate of the number of patients required to determine correlation among the cytokines and growth factor levels, and also correlation with stroke severity and possible disability outcome.

Outcome Variables. The following variables will be collected from the study group. Blood will be collected on admission, 7 14, 30 and 90 days after stroke. We will also collect stroke type – ischemic or hemorrhagic; stroke severity as measured by the NIH stroke scale; stroke outcome as measured by the Ranking scale.

Statistical Analysis. The statistical analysis for this pilot study will be primarily descriptive in nature. The main statistical analysis will employ repeated measures analysis to describe the patterns of change in HMGB-1 and the cytokine values over time. Other techniques will be explored if the data warrant it; such as examining pairs of outcome variables (HMGB-1 and TNF, HMGB-1 and IL-1, or HMGB-1 and stroke severity; as pioneered at Feinstein by Dr. [name] and as in [57]).

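### No pre-stroke disability is recorded, so a correlation of HMGB-1 with the discharge Rankin could mix prior disability with disability caused by this stroke

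*Combined protocol and SAP*

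**What the plan says.** The Introduction states the hypothesis that "persistent HMGB-1 serum levels in patients with stroke retard functional recovery". It treats longitudinal serum data as a first step and says that comparing functional outcome between patients whose inflammation wanes and those in whom it persists will be important.

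Under Research Design and Methods, the data list for stroke patients has one disability item: stroke outcome on the Rankin scale, "measured at admission & discharge". The history items are "Stroke risk factors (history of hypertension, smoking, estrogen supplements") and concurrent infection. The rest are age, gender, stroke type, location and NIH Stroke Scale severity, plus contact details and record number. Pre-stroke function, prior stroke and prior disability do not appear.

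Eligibility is open: "All patients admitted to the stroke service at Northwell will be eligible for inclusion in this pilot study", with age under 18 as the only exclusion.

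In the statistical section, Outcome Variables includes "stroke outcome as measured by the Ranking scale", with no timing or reference state. Specific Statistical Aims says the data will allow a later study to be sized for correlations among the markers and "also correlation with stroke severity and possible disability outcome". Statistical Analysis is primarily descriptive, and its repeated-measures analysis covers HMGB-1 and the cytokines.

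**The concern.** A Rankin grade describes how disabled a person is, not what caused the disability. In a consecutive, unselected stroke series some patients may already be disabled by an earlier stroke or another illness. Their discharge grade carries that disability forward. Read as the result of this stroke, it overstates what the stroke did.

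The link at stake is the one between HMGB-1 and disability. If prior disability is unrelated to HMGB-1, it adds noise and weakens the correlation. If the illness behind it also raises HMGB-1, it could create or inflate an association in the hypothesised direction without any effect on recovery. The documents do not say which applies, and the plan collects nothing with which to find out. Either error would pass into the size of the later study.

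**Working it through.** The plan states no figure that depends on the Rankin scale, and its sample size is one of convenience, so there is nothing to reproduce. The check is whether the collected items can separate prior from new disability, and how much this could matter.

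**1. Which state the admission grade describes.** It is labelled stroke outcome, it is measured, and one phrase governs both admission and discharge. At discharge only the current state is possible. The ordinary reading is current state at both times, although this is not stated.

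**2. Can the collected Rankin grades separate the two kinds of disability?** Take two hypothetical patients (higher is worse):

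| | Pre-stroke (not collected) | Admission | Discharge | Added by this stroke |
|---|---|---|---|---|
| Patient A | 0 | 4 | 3 | 3 − 0 = 3 |
| Patient B | 3 | 4 | 3 | 3 − 3 = 0 |

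The recorded grades are identical. The NIH Stroke Scale grades neurological deficit and does not record function before the stroke. Adjusting for admission Rankin or NIH Stroke Scale therefore does not solve the problem.

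**3. How many patients.** The documents give no prevalence. Let q be the share with pre-stroke Rankin of 3 or more, and assume that no one leaves less disabled than before the stroke. At least 100 × q of the 100 patients are then graded 3 or worse at discharge whatever this stroke did:

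- q = 5%: 5 patients
- q = 10%: 10 patients
- q = 20%: 20 patients
- q = 30%: 30 patients

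**4. Illustration of dilution (all inputs assumed).** In a simulation of 400,000 patients per row:

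- The pre-stroke grade is 3 or 4 with probability q, otherwise 0 or 1, and is independent of HMGB-1.
- The acute grade is a rounded normal with mean 3 and SD 1.2, limited to 0–5. The admission grade is the worse of acute and pre-stroke.
- Recovery in grades is 1.2 − 0.5 × (standardised HMGB-1) + 0.8 × noise, rounded and not below 0.
- The discharge grade is admission minus recovery, but never better than pre-stroke.

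| q | Correlation of HMGB-1 with discharge Rankin | Share of those at 3 or worse who were already there before the stroke |
|---|---|---|
| 0 | 0.284 | 0% |
| 10% | 0.248 | 26% |
| 20% | 0.223 | 44% |
| 30% | 0.199 | 58% |

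The sample size needed to detect a small correlation varies roughly as 1/r². Against the first row, a later study would need about (0.284/0.248)² = 1.3, (0.284/0.223)² = 1.6 and (0.284/0.199)² = 2.0 times as many patients. These figures show direction and order of size only. They are not estimates for this study, and they cover dilution, not confounding.

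**The case against.** The strongest reply is that the pilot makes no claim about disability. Its endpoints are HMGB-1, the cytokines and BDNF, the analysis is mainly descriptive, and disability enters only as a possible correlate for a later study. The exploratory pairs named are HMGB-1 with TNF, with IL-1 and with stroke severity, not with Rankin. This stands, and it limits the reach of the point. It does not remove it, because sizing a later correlation with disability is a stated use of these data and Rankin is the only disability measure available for it.

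It can also be said that the gap is recoverable, since record numbers are collected and existing health records are a source of material. That is partly right for the study team, although nothing ensures that prior function is charted. It does not help outside investigators, who receive banked samples and clinical data fully de-identified.

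Two stronger readings are tempting and should not be adopted.

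- **Sign reversal.** A reader might infer that the change from admission to discharge reverses sign, because an admission grade could describe the state before the stroke or the state in bed. With 0 before, 5 on admission and 3 at discharge, the change is 3 − 0 = +3 or 3 − 5 = −2. The arithmetic is right, but no change score is defined or planned, and reversal between patients would need mixed grading, which nothing in the documents shows. If the admission grade were uniformly pre-stroke, prior disability would be recorded and the present point would fall away.
- **Prior disability counted as poor recovery.** A reader might infer this as fact. No passage classifies recovery from the Rankin scale.

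The idea that chronic illness raises HMGB-1 in these patients is also only a possibility, and the documents do not establish it.

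**Conclusion.** The point holds as a modest, inexpensive improvement. On the ordinary reading of the admission grade, the plan has no variable that separates disability present before the stroke from disability caused by it, and already disabled patients are eligible. An unadjusted correlation of HMGB-1 with discharge Rankin could be diluted or confounded as a result.

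The size is unknown. The range of 5 to 30 patients in 100 follows from an assumed prevalence of 5% to 30%, and the correlations shown rest wholly on assumed inputs. The consequence is confined to the exploratory disability correlation, its bearing on the recovery hypothesis and the planning of a later study. The HMGB-1 and cytokine endpoints, the repeated-measures analysis, the comparison with controls and the convenience sample of 100 are not affected.

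**What to change.** 1. In the data list for stroke patients, add a pre-stroke Rankin grade obtained at consent from the patient, family or chart, and record which source was used.
2. State there that the admission and discharge Rankin scores grade the patient's current state.
3. In the statistical section, state that any exploratory analysis of HMGB-1 against disability will adjust the discharge Rankin for the pre-stroke Rankin, or be repeated in patients with pre-stroke Rankin 0–1. The restricted analysis is a useful companion because a covariate does not undo the limit that prior disability places on how good the discharge grade can be.

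The cost is one history or chart item per patient and one covariate or restriction, with no added visit, blood draw or assessor. Relatives are often already involved in consent when the patient lacks capacity. The drawbacks are that the pre-stroke grade is recalled and sometimes proxy-reported, and that restriction reduces the number analysed.

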production of antigen presenting cells (APCs), lymphocyte infiltration and the expression of co-stimulatory molecules like CD80 [47]. Some experimental pre-clinical evidence suggests that T- and B- cell deficient mice have reduced lesion size after exposure to experimental stroke [48], and progress in delineating mechanism has ruled against antigen recognition, or T-cell receptor co-stimulation, or thrombus formation [49]. But the mechanism for stroke exacerbation caused by humoral and adaptive immune response is not clear. Nor is it clear that the adaptive response is only to exacerbate the ischemia, as experiments with regulatory T cells and IL-17 for example, demonstrate an anti-inflammatory response [50, 51]. Lurking in the literature though, is the persistent rise of HMGB-1 levels and pre-clinical experiments show the rise continues for weeks to months. We believe this persistent pro-inflammatory signal represented by increased serum HMGB-1 needs investigation.

Progress Report/Preliminary Studies

To that end, it is important to note that the medicine group at Northwell, under the guidance of the [name] group at Feinstein, has assayed the HMGB-1 levels in serum samples collected from some patients with brain and cardiac ischemia [52, 53]. Their data show that collection of acute blood samples in the Northwell is possible and, importantly for the purpose of this protocol that the some stroke and cardiac patients have elevated HMGB-1 serum levels hours after the ictus (**Fig 1A & B**). The variable serum levels of HMGB-1 are due to different assays, currently there is a standard ELISA kit for HMGB-1 analysis in the serum (IBL-International, Toronto; ST51011). Of note, the levels of HMGB in serum from age-matched healthy controls were typically less than 20ng/ml of HMGB-1 [5]. Importantly the level of HMGB-1 increased significantly with patients who had their blood sampled after longer times from the onset of their stroke (**Fig 1C**). The progression and persistence of HMGB-1 is not known in the clinical literature, although [name]'s lab has demonstrated that HMGB-1 levels persist in sepsis experiments for weeks (see **Fig 2**).

[figure not shown]

Fig 1A. Stroke patients (N=8) had significantly higher HMGB1 serum concentrations than controls. Patients were included into the study within 24 h after onset of symptoms.
Fig 1B. Stroke patients (N=7) had significantly higher HMGB1 serum concentrations than controls.

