Fig 1C. HMGB serum levels rise as a function of symptom onset. Serum from patients with myocardial infarction (N=9) and cerebral ischemia (N=7) obtained on arrival in the emergency department and correlated with the historical onset of symptoms ($R^2= 0.49$, $P<0.01$).

[figure not shown]
[figure not shown]
[figure not shown]

Fig 2. Animals exposed to severe sepsis (standard cecal ligation and puncture; N=50) demonstrate persistent elevation of HMGB-1 serum measurements.

In an animal model we have been exploring the effect of severe sepsis using a standard stress of cecal ligation and puncture (CLP) on the brain. HMGB1 levels do not rise immediately following CLP but an elevation is sustained for several weeks, making it an ideal therapeutic target. These preliminary results support a rationale for the proposed protocol.

Sepsis is a common clinical problem with a 30% acute mortality, but the survivors do not return to work and sustain loss of both cognitive function and immunocompetence [54-56]. To understand the persistent cognitive impairment in sepsis survivors, we subjected mice to sepsis induced through cecal puncture and ligation (CLP). At 4 weeks following CLP sepsis, mice displayed a loss of long term potentiation (LTP) in hippocampal slice preparations; a measure that can be taken as a loss of synaptic plasticity (**Fig3A**). Also on histologic analysis these animals demonstrated a loss of dendritic arborization and spine density in CA1 neurons of the hippocampus (**Fig 3B**). To ask whether these deficits were a consequence of systemic immune activation, we measured the performance of mice treated with severe sepsis and sham exposed mice on a clock maze. The latency of a mouse's escape is generally thought to depend on memory, and is further thought to be mediated in part by hippocampal neuronal function. **Fig 4A** depicts the performance of mice exposed to severe sepsis and demonstrating memory impairment. In another experiment (**Fig4B**), we treated mice exposed to CLP sepsis for one week with antibody to the inflammatory cytokine HMGB1, beginning one week following CLP. Antibody-treated mice displayed partial improvement in cognition, demonstrating that prolonged systemic inflammation contributes to the post-sepsis cognitive decline and suggesting a therapeutic strategy for neuroprotection in sepsis survivors.

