The Tissue Donation Program (TDP) collects and stores biological samples and associated clinical data as a resource for investigators in the Northwell Health System. Through the development and implementation of tissue specific sub-protocols, these materials may be available to the larger biomedical community. A portion of each blood sample collected for this study will be stored by the TDP and made available for future research according to TDP established procedures.

Plasma will be stored from each blood sample collected. DNA will be isolated and stored once on each patient with stroke at the time of the first blood collection. If for some reason this is not possible, a DNA sample will be isolated from the next available blood sample.

These samples stored by the TDP can be shared by other investigators who submit protocol for use of stored samples to the TDP's Committee for Participant Protection (COPP). Once approved by the COPP, stored samples and associated clinical data can be distributed to the investigator in a completely de-identified fashion. Investigators receiving samples will not have access to the link between a bar coded label and subject identity.

Statistical Considerations and Data Analysis

Specific Aims:

1. Measure the levels of HMGB-1 in patients with stroke. Because the level of HMGB-1 in healthy control subjects is negligible and because survivors of sepsis had levels of HMGB-1 < 20 ng/ml, we believe it is reasonable to assume that levels above 20ng/ml are not normal [5]. Also we are collecting longitudinal samples and we expect that if the pro-inflammatory condition clears in these patients with stroke the HMGB-1 level will fall below 20 ng/ml if not lower.

2. Measure the level of downstream pro-inflammatory molecules and growth factor. We will measure IL-1, IL-6, IL-8, IL-10, TNF and BDNF, all molecules known to be stimulated by HMGB-1 secretion. If we find that HMGB-1 is elevated we expect to find elevations in the other

molecules. If HMGB-1 is not elevated it will be important to measure the serum level of the other cytokines to insure that some other pathophysiology of stroke and stroke recovery is not also involved in activating cytokines. The serum growth factor BDNF level may change in an alternate direction.

Endpoint Variables:

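### Elevated HMGB-1 is read against a literature value of 20 ng/ml that the plan never checks against its own healthy controls

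*Combined protocol and SAP*

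**What the plan says.** All references are to the combined protocol and SAP.

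- **Cutoff for abnormal.** Statistical Considerations and Data Analysis, Aim 1, gives two reasons in one sentence. It opens with "Because the level of HMGB-1 in healthy control subjects is negligible" and continues with "survivors of sepsis had levels of HMGB-1 < 20 ng/ml, we believe it is reasonable to assume that levels above 20ng/ml are not normal", citing reference 5. That reference is dated 1999 and its title describes a mouse endotoxin study.
- **Clearance.** The next sentence is worded as an expectation: "if the pro-inflammatory condition clears in these patients with stroke the HMGB-1 level will fall below 20 ng/ml if not lower".
- **Operational use.** Research Design and Methods makes the same value a trigger for the other assays: "We will measure HMGB-1 and if the levels are elevated (>20ng/ml) we will return to the banked samples in the bio-repository".
- **Healthy levels and assay.** Progress Report/Preliminary Studies says that age-matched healthy controls were typically under 20 ng/ml, again from reference 5. It also says "The variable serum levels of HMGB-1 are due to different assays" and names the ELISA kit now regarded as standard.
- **Controls.** Research Design and Methods plans one sample from up to 30 healthy controls; Sample Size Considerations says 30. They are assayed for HMGB-1 and the other molecules to establish baseline values: "We predict that cytokine levels will be negligible in healthy subjects and their samples will serve as a control for individuals post-stroke".
- **Main analysis.** Statistical Analysis is mainly descriptive, with repeated-measures analysis of the measured values over time.

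**The concern.** Specific Aims sets out to learn when and for how long HMGB-1 is raised, and Sample Size Justification gives the pilot's purpose as finding out whether it is raised at all. Both need a reference level, and 20 ng/ml is the only one offered. Its support is thin in three ways.

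1. No sample size, spread or percentile accompanies it, so nobody can say what share of healthy people lies above it.
2. Being below 20 ng/ml after surviving sepsis does not make a value normal. The Progress Report itself describes survivors as losing cognitive function and immune competence.
3. The protocol attributes variation in HMGB-1 to the assay, yet shows no link between 20 ng/ml and the kit it will use.

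If 20 ng/ml lies well above healthy values, patients who are still raised would be described as normal or cleared, which would hide the persistent state the study is looking for. If it lies inside the healthy range, normal people would be described as inflamed. The controls who could settle this are already planned.

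**Working it through.** **Step 1: can 20 ng/ml be reproduced?** No. The documents give no control mean, SD, percentile or sample size for HMGB-1, and the study sample is one of convenience with no power calculation. No replacement limit in ng/ml can be computed either.

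**Step 2: do the two descriptions of healthy levels agree?** Specific Aims and Statistical Considerations call them negligible, which puts 20 ng/ml far above normal. The Progress Report says typically below 20 ng/ml, which allows it to be near the edge of normal. To see how much this matters, assume log-normal control values with median m and log-SD s. Both are my assumptions; neither is in the documents.

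- 95th percentile = m × exp(1.645 s)
- share above 20 = 1 − Φ(ln(20/m)/s)

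| Assumed median (ng/ml) | 95th percentile, s = 0.6 | 95th percentile, s = 0.4 to 0.8 | Share above 20, s = 0.6 |
|---|---|---|---|
| 2 | 2 × exp(0.987) = 5.4 | 3.9 to 7.5 | 0.01% |
| 10 | 10 × exp(0.987) = 26.8 | 19.3 to 37.3 | 12% |

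In the first row a patient at 10 to 19 ng/ml counts as not elevated at 5 to 9.5 times the healthy median (10/2 and 19/2). In the second, about one healthy person in eight counts as abnormal. The rows point in opposite directions, so they show sensitivity and not a bias of known sign.

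**Step 3: what can 30 controls deliver?**

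- *Without a distributional model.* The 95th percentile falls at rank 0.95 × 31 = 29.45 of 30. The largest of 30 values is at or above the true 95th percentile with probability 1 − 0.95^30 = 78.5% (64.2% with 20 controls). Reaching 95% confidence takes 59 controls. The 97.5th percentile falls at rank 0.975 × 31 = 30.2, outside the data.
- *With a log-normal model.* The 90% confidence limits for the 95th percentile use k = t′(c; n−1, 1.645√n)/√n, where t′ is the noncentral t quantile at c = 0.05 and 0.95. At n = 30 they run from mean + 1.25 SD to mean + 2.22 SD on the log scale. The ratio of upper to lower limit is exp((2.22 − 1.25) × s): 1.47 at s = 0.4, 1.79 at s = 0.6 and 2.64 at s = 1.0.
- *Checking 20 ng/ml directly.* If none of 30 controls exceeds it, the one-sided 95% upper bound on the healthy share above it is 1 − 0.05^(1/30) = 9.5%. With 20 controls it is 13.9%.

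**Step 4: repeated sampling.** Each patient gives up to five samples. If these were independent, the chance that a person with normal levels exceeds a 95th-percentile limit at least once is 1 − 0.95^5 = 23%. Positive correlation within a person would lower this.

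**Step 5: is the assay trigger consistent?** Research Design and Methods makes the other assays conditional on HMGB-1 above 20 ng/ml. Specific Aims, item 2, credits that cutoff with only some support and prefers to analyse all samples. Statistical Considerations, Aim 2, wants the other cytokines measured even when HMGB-1 is not raised. These passages do not agree.

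**The case against.** The strongest reply is that little in the analysis depends on the cutoff. The main method works on measured levels, and Aim 3 compares patients with concurrent controls. A patient at 15 ng/ml would appear in both. This stands and limits the point to the interpretation of elevation and to the assay trigger.

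A reader might also infer more than the documents support:

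- *That the cutoff rests on sepsis survivors alone.* The sentence in Aim 1 begins with healthy levels, and the Progress Report adds a healthy-control basis, although from the same reference.
- *That survivors below 20 ng/ml are known to be still inflamed.* The weeks of raised HMGB-1 are in mice, as is the antibody experiment described as "demonstrating that prolonged systemic inflammation contributes to the post-sepsis cognitive decline". The documents do not say when the human survivors were sampled.
- *That the cutoff predates the study assay.* The reference is dated and the kit is not. All that can be said is that no link between them is shown.
- *That counts of persistently elevated patients, or time to clearance, follow from 20 ng/ml.* The plan defines no such endpoint. Clearance is a prediction that allows for a lower value: "the HMGB-1 level will fall below 20 ng/ml if not lower".

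Finally, a control-based limit has weaknesses of its own. It is imprecise, the controls are a selected group, and five samples per patient give repeated chances to cross it. These objections stand as costs to declare. They do not make an unreferenced 20 ng/ml the better primary limit.

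**Conclusion.** The point holds in a limited form. The only numerical definition of elevated HMGB-1 is a literature value with no stated distribution, part of its support comes from a group that is not healthy, and it is neither shown to apply to the study kit nor checked against controls who will be measured anyway. What is exposed is the statement of whether and how long HMGB-1 is elevated, together with the decision on which samples receive the downstream assays. The repeated-measures description and the Aim 3 comparison are unaffected.

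The direction and size of any misclassification are unknown. The span of healthy 95th percentiles from 3.9 to 37.3 ng/ml rests on assumed medians of 2 and 10 ng/ml and log-SDs of 0.4 to 0.8, and does not show that 20 ng/ml is too high or too low. The precision figures for the control-based limit rest on log-normality and, unless stated otherwise, on all 30 controls being recruited. The change is worth making because it is cheap and bears on the pilot's stated question.

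**What to change.** **In Statistical Considerations, Aim 1:**

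1. Report HMGB-1 at each time point as a continuous level against the study's own controls, assayed with the same kit.
2. Define elevated by a pre-specified upper limit from those controls, for example the log-scale 95th percentile with its confidence interval, and state how values below the detection limit are handled.
3. Report the share of controls above 20 ng/ml with an exact interval, and keep 20 ng/ml as a sensitivity cutoff for comparison with published work.
4. Drop the sepsis-survivor argument as evidence of normality.

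**In Research Design and Methods:** reconcile the trigger for the downstream assays with Specific Aims, item 2, and Statistical Considerations, Aim 2, so that one rule applies throughout.

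**Cost.** Wording and a short calculation, with no new blood samples. If the reconciled rule is to assay every sample, the assay workload exceeds that under the conditional rule.

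**Limitations to state with the results.** At n = 30 the 90% interval for the limit runs from about mean + 1.25 to mean + 2.22 log-SD, and it widens with fewer controls. Controls are screened free of hypertension, smoking, estrogen supplements and concurrent infection while patients are not, so values above the limit may partly reflect those differences. With five samples per patient, a single value above the limit is weak evidence of elevation (up to about 23% of people with normal levels under independence), so results should be shown by time point.
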